## **Exploratory analyses**

The first pre-defined exploratory analysis will compare the exploratory arm with the two other arms. More specifically it will test the two following hypotheses: The exploratory arm confers similar or greater benefit compared to the interventional arm and greater benefit compared to the control arm.

The second hypothesis generating exploratory analysis will examine how the changes in leptin measurements correlate with changes in weight overall and by intervention arm. Leptin will be measured via saliva samples at weeks 0, 6, 12 and 26.

The last exploratory analysis will examine how outcomes in the exploratory arm vary across adherence levels. Adherence levels will be defined from the recorded activity of the application.

These analyses are exploratory in nature hence results will be interpreted cautiously.

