For each of the primary and secondary outcomes, formal statistical analysis will be based on appropriate linear models. From each linear model, an estimate of the magnitude of the treatment effect i.e. the difference in mean outcomes between the control arm and intervention arm, will be derived, together with adjusted (least squares) means, 95% confidence intervals, and associated p-values. Initial exploratory analyses of these models will include relevant baseline covariates, including baseline values of the endpoint, and

all covariates that are statistically significant will be retained in the model for the purposes of deriving the final treatment effect outcomes. Baseline values of the endpoint will be retained in each model regardless of statistical significance.

All analyses will be conducted using two-sided tests and at a significance level of 5%.

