## 1.9 Analyses of quantitative data

Continuous outcomes will be compared between groups using the modified analysis of covariance (ANCOVA). This approach has been chosen because it is more powerful than other alternatives such as t-test.

A linear regression model will be used to analyse the association between post-intervention values of the outcomes with intervention arm adjusting for their baseline value, participant age and sex.

Let  $y_{it}$  denote the outcome value for individual  $i$  at time  $t$ ,  $x_i$  her covariates (e.g. sex, age) and  $d_i$  her intervention arm. The ANCOVA model is given by:

$$y_{it} = \beta_0 + \beta_1 y_{i0} + \beta_2 x_i + \gamma d_i + \varepsilon_{it}$$

An extension of the basic ANCOVA model will consider an interaction between the intervention indicator and the baseline values to test the assumption that the treatment effect varies with baseline status.

In addition, changes in continuous outcomes from baseline will be analysed using a linear regression model of the difference between the outcome value at visit and its baseline value. Using the same notation, the change model is

$$\Delta y_{it} = y_{it} - y_{i0} = \beta_0 + \beta_1 x_i + \gamma d_i + \varepsilon_{it}$$

Covariates will be centered in the analyses. Robust linear regression *lmrob* from the R package *robustbase* will be used for the ANCOVA analysis unless specified otherwise. It uses the MM-estimator to estimate the regression coefficient accounting for departure from normality of the outcomes.

Assessment of models' goodness of fit will include careful examination of residuals using graphical methods (scatter plot, boxplot and QQ plot) and detection of outliers. In addition, equality of the post-treatment variances will be tested using Levene's test.

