## 1.11 Non-parametric model

For variables showing strong departure from normality, the non-parametric Mann Whitney Wilcoxon rank sum test (two groups) or the Kruskal and Wallis (to compare the three arms) will be used.

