### **1.14 Planned analysis**

The primary analysis will be conducted under the ITT principle using modified ANCOVA as described above. Raw and adjusted mean differences in PFG at week 6 between the intervention and control arm will be presented with 95% confidence interval (95% CI). The adjusted mean difference will be estimated using a linear regression model of week 6 FPG to baseline PFG and treatment arm adjusted for age and sex.

The primary null hypothesis is of no difference in week 6 FPG adjusted means between the intervention and the control arms. It will be tested against the alternative hypothesis of a difference between the two groups.

$$H_0: \mu_0 = \mu_1$$

$$H_A: \mu_0 \neq \mu_1$$

Where  $\mu_0$  and  $\mu_1$  are the week adjusted trimmed mean FPG in respectively the control and intervention group. The null hypothesis will be rejected if the robust adjusted 95% CI of the mean difference does not include 0.

- Power of the analysis

With 60 participants in each group and assuming that the average PFG changes from baseline to the week 6 will be -0.6 mmol/l in the intervention arm and -0.1 mmol/l in the control arm, that the baseline standard deviation (sd) of PFG is 0.7, the post-intervention sd is 0.6, and that the correlation between baseline and post-intervention measurement range between 0.6 and 0.4, the analysis will have a power greater than 0.9 to detect a difference between both arms.

- Sub-group and additional analysis of the primary outcome

An interaction between baseline FPG and treatment effect will be tested.

No sub-group analysis is planned for the primary endpoint.

- Sensitivity analysis

The robustness of the results will be tested using a non-parametric model as described above.

Both results will be presented and discrepancies will be discussed.

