## **Additional information**

### **1.20 Significance level**

All analyses will be conducted using a 5% significance level. No adjustment for multiplicity will be used.

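### The SAP pre-defines a test that the app arm gives similar or greater benefit than the report arm, but has no criterion for similarity and defines only difference tests, which cannot establish it

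*SAP*

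**What the plan says.** The SAP's section on exploratory analyses opens with a pre-defined comparison of the app (exploratory) arm with the other two arms. It announces "More specifically it will test the two following hypotheses", and then: "The exploratory arm confers similar or greater benefit compared to the interventional arm and greater benefit compared to the control arm". The section gives no margin, outcome, time point or decision rule for this. It closes by calling the analyses exploratory and asking for cautious interpretation.

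The inferential tools are set out elsewhere:

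- SAP 1.9 and 1.10 give a baseline-adjusted ANCOVA, a change-from-baseline regression and a linear mixed model.
- SAP 1.11 gives a rank-sum test for two groups; for three, "the Kruskal and Wallis (to compare the three arms) will be used".
- SAP 1.20 says: "All analyses will be conducted using a 5% significance level. No adjustment for multiplicity will be used". It does not state sidedness.
- Protocol 9.4 says: "All analyses will be conducted using two-sided tests and at a significance level of 5"%.
- SAP 1.14 contains the only written decision rule: reject the null if the robust adjusted 95% CI excludes 0. It belongs to intervention versus control at week 6.

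Protocol 9.5 lists what the app data will be used to explore. It gives no similarity criterion either.

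**The concern.** A claim of similar or greater benefit needs evidence that the app arm is not worse than the report arm by more than some stated amount. A difference test asks whether the data are incompatible with zero difference. Failing to reject zero can mean that the arms are close, or only that the interval is wide. With no stated amount, the hypothesis as written has no result that would confirm its similarity part, and the meaning of similar would have to be settled after the data are seen.

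The comparison addresses the app objectives (Protocol 2.3, SAP 1.3), and a real deficit is plausible by design. Protocol section 5 gives the report arm dietitian follow-up calls and the app arm none. The company that supplies the app also funds the trial (Protocol 10.6), which is a further reason to fix the criterion in advance.

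**Working it through.** **Inputs**

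- Planned effect: mean FPG changes of -0.6 and -0.1 mmol/L in the intervention and control arms (SAP 1.14), a difference of 0.5. Half of it is 0.25.
- SDs: baseline 0.7, post-intervention 0.6; correlation ρ from 0.4 to 0.6 (SAP 1.14).
- SD of change: 0.6 (Protocol 9.3).
- n: 60 randomised per arm. Protocol 9.3 raises 50 by 20% to allow for losses, so 50 assessed is the lower case.
- Test: two-sided 5%.
- Assumption: the app arm has the same SDs and correlation as the other arms.

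**Standard deviations**

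- ANCOVA residual SD = 0.6 × √(1 − ρ²): 0.550 at ρ = 0.4, 0.480 at ρ = 0.6.
- Change-score SD = √(0.7² + 0.6² − 2ρ × 0.7 × 0.6) = √(0.85 − 0.84ρ): 0.717 at ρ = 0.4, 0.588 at ρ = 0.6.

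**The plan's own figure.** SAP 1.14 states power above 0.9 for a 0.5 mmol/L difference with 60 per arm. The inputs give 0.999 or more by ANCOVA and 0.969 to 0.997 by change score. The statement reproduces.

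**Chance of a non-significant result when the app is truly 0.25 worse.** SE = SD × √(2/n). To a normal approximation the chance is Φ(1.96 − 0.25/SE), the opposite tail being negligible.

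- SD 0.480, n = 60: SE = 0.0876; 0.25/SE = 2.853; Φ(−0.893) = 0.186. The noncentral t gives 0.192.
- SD 0.550, n = 50: SE = 0.110; 0.25/SE = 2.273; Φ(−0.313) = 0.377. The noncentral t gives 0.386.

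**Non-inferiority power at a true tie.** This uses an illustrative margin of 0.25, which is not in the documents. Power = Φ(0.25/SE − 1.96). For the same two cases: Φ(0.893) = 0.814 and Φ(0.313) = 0.623.

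| Model | SD | Non-significant at 0.25 deficit, n = 60 / 50 (noncentral t) | 95% CI half-width, n = 60 / 50 | Non-inferiority power at a tie, n = 60 / 50 |
|---|---|---|---|---|
| ANCOVA, ρ = 0.6 | 0.480 | 19% / 27% | 0.172 / 0.188 | 81% / 74% |
| ANCOVA, ρ = 0.4 | 0.550 | 31% / 39% | 0.197 / 0.216 | 70% / 62% |
| Change score, ρ = 0.6 | 0.588 | 36% / 44% | 0.210 / 0.231 | 64% / 57% |
| Protocol SD of change | 0.600 | 38% / 46% | 0.215 / 0.235 | 63% / 55% |
| Change score, ρ = 0.4 | 0.717 | 53% / 59% | 0.257 / 0.281 | 48% / 41% |

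At a smaller true deficit of 0.125, the ANCOVA comparison is non-significant in about 70-79% of trials (normal approximation).

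**One possible result.** With SD 0.550 and 50 per arm, an observed app-minus-report difference of +0.10 has a 95% CI of 0.10 ± 0.216, that is −0.116 to 0.316. It is non-significant, yet it does not exclude a loss of half the planned effect.

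**The case against.** Several points on the other side have force.

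- *No rule equates non-significance with similarity.* A reader might infer that a non-significant p-value will pass for similarity. The documents do not say so, and SAP 1.14's rule is for another comparison. This stands. What remains is that the SAP supplies no other criterion.
- *The plan is not limited to p-values.* Raw and adjusted differences with 95% CIs are the output for the primary endpoint, and the SAP's section on secondary endpoints carries the same analyses to the other continuous variables. An app-minus-report interval would be a natural by-product, although it is not spelled out and Protocol 9.4 defines the treatment effect as control versus intervention. This stands, and makes the repair small.
- *Noise does not simply favour the claim.* The hypothesis also requires greater benefit than control, which noise makes harder to show. This stands for the paired claim. The two parts could still be reported separately.
- *The outcome is not wholly unnamed.* The app objectives point to glucose regulation and the secondary outcomes. What is missing is a chosen endpoint and time point for this test.
- *Most half-effect losses would be detected.* By ANCOVA, yes: in about 61-81% of trials. The figures describe a risk and not the expected outcome.
- *This is an exploratory arm of a pilot, and caution is stated.* This stands, and lowers the severity. Caution in interpretation is still not a definition of similar.

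**Conclusion.** The point holds as a mismatch between hypothesis and method. The SAP says it will test similar or greater benefit, has no criterion for similar, and defines only 5% difference tests, which cannot establish it. If a non-significant result were taken as support, a true loss of 0.25 mmol/L would go undetected in about 19-39% of trials by ANCOVA and 36-59% by change score, with 50 to 60 per arm.

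These figures assume that the SAP's SDs and correlation apply to the app arm, that week-6 FPG carries the comparison, that the test is two-sided, and that the planned robust regression performs like ordinary least squares.

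A reader might also infer that a margin-based rule would be comfortably powered at this size. The documents' inputs do not support that in general. At the illustrative margin of 0.25, power at a true tie is 62-81% by ANCOVA, 55-63% at SD 0.6 and 41-64% by change score.

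Severity is low. The analysis is exploratory, and no primary or secondary conclusion depends on it.

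**What to change.** In the SAP's section on exploratory analyses:

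1. Name the outcome and time point for app versus report. Week-6 FPG is a suggestion, since it matches the primary endpoint; the sponsor may prefer another.
2. Report app minus report with its 95% CI from the planned baseline-adjusted model.
3. State that a non-significant difference will not be read as similarity.
4. Choose one of two routes:
   - claim similar or greater benefit only if the unfavourable limit of the CI (the upper limit for FPG) lies within a margin that the sponsor fixes and justifies before the data are seen, and otherwise call the result inconclusive; or
   - drop the word similar and report the estimate with its CI.
5. Keep app versus control as a superiority comparison.

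This changes SAP wording only and needs no new data. The cost is that the similarity claim becomes harder to make. Under the margin route a true tie may often be inconclusive: at 0.25 mmol/L, 80% power would need 58-76 assessed per arm by ANCOVA, 91 at SD 0.6 and 87-130 by change score. If that is unattractive, the second route is enough for an exploratory arm.

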## **Additional information**

### **1.20 Significance level**

All analyses will be conducted using a 5% significance level. No adjustment for multiplicity will be used.

### **1.21 Statistical software**

Data management will be performed using the statistical software Stata version 12.1 (LP StataCorp). Statistical analyses will be performed with the statistical software R (R

Foundation for Statistical Computing). The R packages WRS2, robustbase, lme4 and robustlmm will be used.

